### **1.3.3** *Schedule of assessments*

Here are the schedules of assessments extracted from the current version of the protocol:

**Table 1 Study Schedule of Assessments (dose escalation)**

Procedures and assessments	CORE TRIAL [v]																			EOCT or ED [a]	Long-term Follow-up [b]
	Screening	Treatment Period																			
		Cycle 1									Cycle 2										
	D-21 to D-1 [c]	D1 [d]	D2	D3	D4	D5	D7	D 15	D 22	D29	D1 [e]	D2	D3	D4	D5	D7	D15	D22	D29	D43	
Visit window (days)			+1			+1	±1	±1	+7 (+28) [e]			+1			+1	±1	±1	+7 (+28) [e]	+7	±14	
Informed consent	x																				
Inclusion/exclusion criteria	x	x																			
Subject demographics and height	x																				
Medical and disease history	x																				
ECOG performance status	x	x								x										x	
ceCT/MRI	x [f]																			x	
 F-FDG-PET		x [g]																		x	
 Lu-3BP-227 screening administration	x																				
Tumour biopsy	x [i]																			x	

AE=adverse event; ceCT/MRI=contrast enhanced computed tomography/magnetic resonance imaging; cfDNA=cell-free deoxyribonucleic acid; D=Day; ECG=electrocardiogram; ECOG=Eastern Cooperative Oncology Group; ED=early discontinuation; EOCT=end of core trial; IMP=investigational medicinal product; NTSR1=neurotensin receptor 1; PET=positron emission tomography; PK=pharmacokinetic; SPECT=single photon emission computed tomography.

a the ED visit will take place within 14 days after ED from the study and at the latest 5 weeks after the last IMP administration, the visit will correspond to an EOCT visit. For subjects who received the screening IMP administration and found ineligible to participate to the study, an ED visit will be performed within 5 weeks (+ 2 weeks) after the IMP screening administration to assess the safety. At least, clinical laboratory tests (e.g. haematology and biochemistry), AEs and concomitant medication/therapy will be collected. If the subject is not able to come for an on-site visit, the visit may be performed by phone call. The clinical laboratory tests may be done locally.

b follow-up visits will take place every 3 months (±2 weeks) and will start after the EOCT, ED or EOAC visit. Efficacy will be assessed until disease progression, administration of any other chemotherapy or radiotherapy, lost to follow-up, withdrawal of consent, death or a maximum of 2 years, whichever occurs first (see Section 6.2.3). After disease progression is confirmed, no further CT/MRI scans will be required for tumour/disease assessment. The survival status and safety of the subjects will continue to be monitored as indicated in Section 8.1.2.3 until lost to follow-up, withdrawal of consent, death or a maximum of 5 years, whichever occurs first.

c the screening period can be extended by two weeks if this is required for logistical reasons.

d Day 1 of Cycle 1 is the day of the first treatment administration. Day 1 of Cycle 2 and each potential subsequent cycle may coincide with Day 29 of the previous cycle if all safety assessments are performed and allow for the next administration.

e in case of toxicity requiring a delay, the next treatment administration will be delayed by up to 4 weeks.

f whole body ceCT or ceMRI including brain unless a similar exam has already been performed within 1 month prior to Day -21.

g Cycle 1 Day 1 F-FDG-PET between Day -21 and Day 1.

h screening administration will be done after confirmation of eligibility (i.e. after all other screening assessments have been performed), minimum 1 week before the first treatment administration.

Table 1 Study Schedule of Assessments (dose escalation) (continued)

Procedures and assessments	CORE TRIAL [v]																		EOCT or ED [a]	Long-term Follow-up [b]
	Screening	Treatment Period																		
		Cycle 1									Cycle 2									
D-21 to D-1 [c]	D1 [d]	D2	D3	D4	D5	D7	D 15	D 22	D29	D1 [d]	D2	D3	D4	D5	D7	D15	D22	D29	D43	
Visit window (days)			+1			+1	±1	±1	+7 (+28) [e]			+1			+1	±1	±1	+7 (+28) [e]	+7	±14
 Lu-3BP-227 treatment administration	x									x										
Blood sampling for  Lu-3BP-227 PK [j]	x	x	x		x					x	x	x	x							
Planar scintigraphy [k]	x	x	x	x	x	x				x	x	x	x	x						
SPECT/CT scan [k]	x	x	x	x	x	x				x	x	x	x	x						
Blood sampling for 3BP-227 PK [l]	x	x	x																	
Urine sampling for  Lu-3BP-227 PK [m] and 3BP-227 PK [t]	x	x	x																	

i in case subject consents to have a biopsy and in case it can be accomplished with reasonable safety, a tumour biopsy will be taken during screening from the primary or metastatic lesion, whichever is accessible, ideally on lesions which are positive for NTSR1 on Lu 3BP-227 SPECT/CT following IMP screening administration, as soon as Lu uptake has been confirmed. If not, archival tissue from a previous tumour biopsy can be used for exploratory analysis (tumour microenvironment analysis and transcriptomics).

j eighteen blood samples will be collected during the treatment period. Blood samplings will be performed just before the Lu-3BP-227 infusion (baseline), at the end of infusion (0), 5 minutes ±1 minute, 30 minutes ±5 minutes, 90 minutes ±15 minutes and 4 hours ±30 minutes, 24 hours ±2 hours, 48 hours ±2 hours and 72 to 96 hours post infusion.

k eleven whole body scans (planar scintigraphy) and SPECT/CT acquisitions will be performed during the treatment period. Whole body scans (planar scintigraphy) and SPECT/CT scan will be performed at the following timepoints just after the end of Lu-3BP-227 infusion: Day 1: 4 (±2) hours, Day 2: 24 (±6) hours, Day 3: 48 (±6) hours, Day 4: 72 to 96 hours, and Days 7 to 8: 138 to 168 hours. Within each cycle, a single SPECT/standard dose CT will be performed. A SPECT/low dose CT will be performed at all other timepoints. Details of the procedures will be provided in the Image Acquisition Guidelines. At screening, planar scintigraphy (1 or 2 timepoint(s) at the investigator’s discretion) and optional SPECT/CT scans (up to 2 at the investigator’s discretion) will be performed after screening administration of Lu-3BP-227.

l ten blood samples will be collected at cycle 1. Blood samplings will be performed just before Lu-3BP-227 infusion (baseline), at the end of infusion of Lu-3BP-227 (0), 5 minutes ±1 minute, 30 minutes ±5 minutes, 90 minutes ±15 minutes and 4 hours ±30 minutes, 6 hours ±30 minutes, 8 hours ±1 hour, 24 hours ±2 hours and 48 hours ±2 hours after the end of infusion of Lu-3BP-227.

m four urine samples will be collected during the treatment period at the following time periods and only for Cycle 1: from the start of the IMP infusion to 6 hours, 6 to 12 hours, 12 to 24 hours, and 24 to 48 hours (from the start of the IMP infusion to 6 hours after the end of the infusion only for US sites) after the end of Lu-3BP-227 infusion.

Table 1 Study Schedule of Assessments (dose escalation) (continued)

Procedures and assessments	CORE TRIAL [v]																		EOCT or ED [a]	Long-term Follow-up [b]	
	Screening	Treatment Period																			
		Cycle 1									Cycle 2										
	D-21 to D-1 [c]	D1 [d]	D2	D3	D4	D5	D7	D 15	D 22	D29	D1[d]	D2	D3	D4	D5	D7	D15	D22			D29
Visit window (days)			+1			+1	±1	±1	+7 (+28) [e]			+1			+1	±1	±1	+7 (+28) [e]	+7	±14	
AEs	x	x	x	x	x	x	x	x	x	x	x	x	x	x	x	x	x	x	x	x	x [z]
Physical examination	x	x [y]						x		x	x						x		x	x	
Vital signs	x [n]	x [n]	x	x			x	x	x	x	x [n]	x	x			x	x	x	x	x	
Body weight	x	x [y]						x		x	x						x		x	x	
ECG (12-lead) [o]	x	x	x								x	x								x	
24-hour 3-lead Holter ECG [p]		x									x										
Haematology and biochemistry [w]	x	x [y]					x	x	x	x	x					x	x	x	x	x	x
Urinalysis	x	x [y]	x	x						x	x								x	x	
CCI																					
Prior/concomitant medication/therapy	x	x	x	x	x	x	x	x	x	x	x	x	x	x	x	x	x	x	x	x	x

n prior to and at the end of 177Lu-3BP-227 infusion (0) as well as 30±5 minutes, 90±15 minutes, 4 hours±30 minutes after the end of 177Lu-3BP-227 infusion.  
o during the screening period, a triplicate 12-lead ECG will be recorded before the screening administration (minus 15 minutes), and a single 12-lead ECG will be recorded at the end of 177Lu-3BP-227 infusion (±15 minutes) and 4 hours (±30 minutes) after the end of infusion. At each treatment administration, a triplicate 12-lead ECG will be recorded on Day 1 before the infusion (baseline) (minus 15 minutes) and a single 12-lead ECG recordings at the end of 177Lu-3BP-227 infusion (±15 minutes), at 4 hours after the end of 177Lu-3BP-227 infusion (±30 minutes) and on Day 2 at 24 hours after the end of 177Lu-3BP-227 infusion (±4 hours) as well as at EOCT. All 12-lead computerised standard ECGs will be recorded in the supine position after at least 5 minutes of rest.  
p starting before 177Lu-3BP-227 infusion, a 24-hour 3-lead continuous ECG Holter will be recorded.

Table 1 Study Schedule of Assessments (dose escalation) (continued)

Procedures and assessments	CORE TRIAL [v]																		EOCT or ED [a]	Long-term Follow-up [b]
	Screening	Treatment Period																		
		Cycle 1									Cycle 2									
	D-21 to D-1 [c]	D1 [d]	D2	D3	D4	D5	D7	D 15	D 22	D29	D1[d]	D2	D3	D4	D5	D7	D15	D22		
Visit window (days)			+1			+1	±1	±1	+7 (+28) [e]			+1			+1	±1	±1	+7 (+28) [e]	+7	±14
Pregnancy test [q]	x	x								x									x	
Hormone analysis [r]	x																		x	
CCI	[REDACTED]																			
Tumour markers in serum		x								x									x	
CCI	[REDACTED]																			
Survival status																				x

q serum pregnancy test will be performed at the screening visit. A urine pregnancy test will be performed on Day1 prior to IMP administration and at EOCT/ED.

r sample for hormone analysis (NTSR1 organ expressing) should be taken at the closest to 08:00.

s CCI [REDACTED]

t four urine samples will be collected during the treatment period at the following time periods and only for Cycle 1: from the start of the IMP infusion to 6 hours, 6 to 12 hours, 12 to 24 hours, and 24 to 48 hours after the start of 177Lu-3BP-227 infusion (from the start of the infusion to 6 hours after the end of the infusion only for US sites).

u CCI [REDACTED]

v if an additional cohort of subjects is recruited to receive 3 cycles of therapy as described in the Study Design (dose escalation part Phase I), the schedule of assessments for the third cycle of therapy is to be the same as the schedule of assessments for Cycle 2.

w additional safety assessments including haematology and biochemistry can be done if clinically indicated.

x urine samples will be collected (and frozen) at the following timepoints: Cycle 1: Day 1: early morning, before the infusion (baseline), Day 3: early morning (48 hours after the end of 177Lu-3BP-227 infusion at the latest) and EOCT/ED: early morning.

y on Day 1, assessments to be done predose and up to 48 hours before IMP infusion.

z Any AEs/SAEs, irrespective of causality, are to be reported to the sponsor up to 6 months after the EOCT, ED or EOAC visit or until new antitumour treatment starts, whichever comes first. After this timepoint, up to the end of the 5-year follow-up period, AEs/SAEs should only be reported if the event is evaluated as related to the IMP or study procedure by the investigator.

Table 2 Study Schedule of Assessments (additional cycles in case of clinical benefit and good tolerability)

Procedures and assessments	Additional cycles									EOAC or ED [g]
	D1	D2	D3	D4	D5	D7	D15	D22	D29	D43
Visit window (days)			+1			+1	±1	±1	+7 (+28)	+7
ECOG performance status	x									x
ceCT/MRI [a]									x	x
 F-FDG-PET										x
 Lu-3BP-227 treatment administration	x									
Planar scintigraphy [b]	x	x	x		x	x				
SPECT/CT scan [b]	x	x	x		x	x				
Blood sampling for  Lu 3BP-227 PK [c]	x	x	x		x					
AEs	x	x	x	x	x	x	x	x	x	x
Physical examination	x								x	x
Vital signs	x [d]	x	x			x	x	x	x	x
Body weight	x						x		x	x
ECG (12-lead) [e]	x									x
Haematology and biochemistry	x	x				x	x	x	x	x
Urinalysis	x								x	x
Prior/concomitant medication/therapy	x	x	x	x	x	x	x	x	x	x
Pregnancy test [f]	x									x
Tumour markers in serum	x									x

AE=adverse event; ceCT/MRI=contrast enhanced computed tomography/magnetic resonance imaging; D=Day; ECG=electrocardiogram; ECOG=Eastern Cooperative Oncology Group; EOAC=end of additional cycles; IMP=investigational medicinal product; PET=positron emission tomography; PK=pharmacokinetic; SPECT=single photon emission computed tomography.

- ceCT/MRI will be done every 2 cycles during additional administrations, to confirm the clinical benefit after 2 additional administrations (i.e. at Cycle 4 and EOAC). In case of early discontinuation, the ceCT/MRI should be performed at the ED visit, to confirm any disease progression.
- full dosimetry assessment will be performed after the first and third additional administrations as described for Cycles 1 and 2. After the second and fourth additional administrations, only a single SPECT/standard dose CT at 48 (±6) hours will be performed
- After the first and the third additional administration, blood samplings will be performed just before Lu-3BP-227 infusion (baseline), at the end of infusion of Lu-3BP-227 (0), 5 minutes ±1 minute, 30 minutes ±5 minutes, 90 minutes ±15 minutes and 4 hours ±30 minutes, 24 hours ±2 hours and 48 hours ±2 hours, and 72 to 96 hours ±2 hours. After the second and fourth additional administrations a single blood collection will be performed at 24 hours only (as close as possible to the SPECT/CT).
- prior to and at the end of Lu-3BP-227 infusion (0) as well as 30±5 minutes, 90±15 minutes, 4 hours±30 minutes after the end of Lu-3BP-227 infusion.
- at each cycle, a triplicate 12-lead ECG will be recorded on Day 1 before the infusion (baseline) (minus 15 minutes). A single 12-lead computerised standard ECG, with paper printout, will be recorded in supine position after at least 5 minutes of rest during each cycle on Day 1 at the end of Lu-3BP-227 infusion (±15 minutes) and at 4 hours (±30 minutes) after the end of Lu-3BP-227 infusion as well as at EOAC.
- a urine pregnancy test will be performed on Day 1 prior to IMP administration.
- the ED visit will take place within 14 days after ED from the study and at the latest 5 weeks after the last IMP administration.

### 1.3.4 **Planned sample size**

As this is primarily a descriptive safety and tolerability study, the total number of subjects is not based on a formal statistical sample size calculation.

The actual sample size required to adequately determine the MTCA/ Maximum Tolerated Single Activity (MTSA) during dose escalation depends on the initial dose, rate of dose escalation and the observed dose-toxicity and dose/radiation exposure relationships. Simulation studies have been performed to quantify the operational characteristics (i.e. precision of the MTCA/MTSA, sample size, number of subjects being over/under dosed) of the adaptive dose-escalation design under a number of plausible dose-DLT relationship scenarios. Based on experience, the chosen sample size of three to five subjects per cohort is considered sufficient to fulfill the objectives of the study. It is anticipated that approximately 30 subjects will be required to establish the MTCA or Maximum Administered Cumulative Activity (MACA).

## 2 **SUBJECT POPULATIONS (ANALYSIS SETS)**

### 2.1 **Screened population**

The screened population is all screened subjects in the study i.e. who signed the informed consent.

### 2.2 **Included population**

The included population is all screened subjects who are included in the study and received the therapeutic dose.

### 2.3 **Safety population**

The safety population is all subjects who received at least one dose of study medication (including screening administration).

### 2.4 **Pharmacodynamic/Efficacy population**

#### 2.4.1 **Pharmacodynamic population**

The pharmacodynamic population is all subjects who received at least one therapeutic dose and with available post-baseline pharmacodynamics/efficacy data.

#### 2.4.2 **Primary pharmacodynamic population**

The primary pharmacodynamic population for tumour response is all subjects who have received at least two therapeutic doses of Lu-3BP-227 and reached the end of Cycle 2 or EOCT visit with available post-baseline tumour assessment based on RECIST criteria v1.1 and with no major protocol deviations with an impact on the analysis.

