Serum and whole blood ribonucleic acid samples will be stored for further biomarker analysis after the end of the study. Analysis of additional biomarkers from the biobank samples will be performed outside the scope of the main study and reported separately.

Statistical methodology

Statistical methodology in phase I

Safety

Continued monitoring of DLTs and toxicities will be performed during dose escalation. At the time of the SRC, an interim analysis of the DLTs, toxicities

and selected organ absorbed doses (kidney, liver and bone marrow) will be performed to guide the dose selection during the dose escalation part.

Biodistribution, radiation dosimetry, PK of ¹⁷⁷Lu-3BP-227

Descriptive summaries of PK and biodistribution parameters will be presented for each cohort over the treatment period.

Pharmacokinetics of 3BP-227

If 3BP-227 levels are measurable in plasma and urine, PK parameters of 3BP-227 will be derived using a noncompartmental approach. An attempt to build an integrated model taking into account PK, dosimetry, antitumour and safety data will be made.

Pharmacodynamics/Efficacy Analysis

In order to perform preliminary antitumour activity, ORR and DCR will be tabulated. Tumour response will be evaluated by the site investigator. Independent review of tumour assessment may be requested at the discretion of the sponsor. In both cases, response and progression will be evaluated using the revised RECIST guideline (version 1.1). Only subjects with measurable disease at baseline, who have received at least two administrations of ¹⁷⁷Lu-3BP-227 and reached the end of Cycle 2 or EOCT visit will be considered evaluable for response.

Statistical methodology in phase II

Efficacy Analysis

For phase II cohorts, tumour response will be assessed in imaging modalities of CT or MRI scans after Cycle 2 and subsequently every 8 weeks for the first 6 months and every 12 weeks thereafter. Images will be reviewed by an independent central review core laboratory. ORR, best overall response (BOR) and other efficacy parameters will be tabulated. Objective response rate will be calculated combining the number of subjects with a BOR of confirmed complete response (CR) or partial response (PR) per RECIST version 1.1.

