4.4.2 Secondary Endpoints

4.4.2.1 Phase I

For biodistribution and dosimetry of ¹⁷⁷Lu-3BP-227, the secondary endpoints are:

- Maximal uptake (%), maximal concentration achieved (C_{max}); time post injection to achieve maximal concentration (T_{max}); AUC at the target lesions, discernible organs and blood; t_{1/2} of activity concentrations in blood;
- Highest absorbed dose, specific absorbed dose to the target lesions (Gy/GBq), specific absorbed dose per organ (Gy/GBq) and cumulative absorbed organ doses (Gy).

For PK of 3BP-227, the secondary endpoints are:

• PK parameters including, but not limited to, C_{max}, AUC, t_{1/2}, CL, V_d, cumulative amount of unchanged drug excreted into the urine (Ae), renal clearance of the drug from plasma (CL_R), as measured in plasma and urine at defined timepoints.

For pharmacodynamics, the secondary endpoints are:

- Objective response rate and DCR, as determined by RECIST version 1.1 in subjects who received IMP;
- Progression-free survival (PFS) and OS rates as determined from start of study treatment until occurrence of event and/or end of observation period;
- Evaluation of metabolic tumour response using PERCIST (version 1.0) or practical PERCIST;
- Changes in serum tumour markers relevant and specific to the underlying tumour disease from baseline to EOCT, which is planned 6 weeks after the second ¹⁷⁷Lu-3BP-227 dose administration.

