4.7 Discontinuation Rules

4.7.1 Individual Discontinuation Rules

In accordance with the Declaration of Helsinki and the applicable country's regulations, each subject is free to withdraw from the study at any time and for any reason without prejudice to their future medical care by the investigator at the institution.

The investigator will be responsible for monitoring subject compliance. A subject can be withdrawn from the study at any time if the investigator or the sponsor determines that the subject is not in compliance with the study protocol.

The investigator has the right to withdraw a subject from the study in the event of concurrent illness, AEs, or other reasons concerning the health or well-being of the subject, or in the case of lack of cooperation.

If any of the following occur, no further treatment will be administered:

- life-threatening toxicities outside of the DLT reporting period
- subject withdraws their consent to further treatment;
- cumulative kidney dose exceeds 23 Gy;
- cumulative bone marrow dose exceeds 2 Gy, as determined by dosimetry of peripheral blood samples and imaging;
- cumulative liver dose exceeds 30 Gy;
- occurrence of a DLT for phase I dose escalation only (see Section 4.7.1.1).

All cases of discontinuation will be discussed between the investigator and the sponsor.

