6.2.2 Treatment Period and Additional Cycles for Phase I Dose Escalation

The visit descriptions in this section are relative to the phase I dose escalation part of the study. In case of phase I dose expansion and for phase II, these visits and timepoints will be amended in light of the phase I results.

After each administration of IMP/¹⁷⁷Lu-3BP-227, subjects may be hospitalised for at least 24 hours for observation at the investigator's discretion. Afterwards, subjects can be discharged when the radioactivity reaches an acceptable level as per local regulation. The subjects must return to the study centre for further evaluations per the schedule of assessment. All other visits will be outpatient. Subjects are to be observed on study and if the disease comes under control are to be kept on study; if the disease does not appear to come under control, the subject is to be removed from study and treated as clinically indicated.

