12.1 Analysis Sets

For dose escalation only, all subjects who complete Cycle 2 or discontinue during Cycle 1 or Cycle 2 due to a DLT will be included in the MTCA and MTSA evaluations.

For the overall study, all subjects who received at least one dose of the IMP will be included in the safety evaluation. All subjects who receive at least one dose of IMP and who have postbaseline efficacy data will be included in the efficacy evaluations. All subjects with evaluable 3BP-227 PK data and no major protocol deviation with an impact on PK analysis will be included in the evaluation of 3BP-227 PK. All subjects with evaluable dosimetry images and no major protocol deviation with an impact on dosimetry analysis will be included in the evaluation of dosimetry. All subjects with evaluable blood or urine dosimetry data and no major protocol deviation with an impact on ¹⁷⁷Lu-3BP-227 PK analysis will be included in the evaluation of ¹⁷⁷Lu-3BP-227 PK. Major deviations will be described in a specific document.

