12.2.7 Pharmacodynamic/Efficacy Evaluation

For phase I, tumour response will be evaluated only by the site investigator, using the revised RECIST guideline version 1.1 (see Attachment 4, Section 19.4). Only subjects with measurable disease at baseline, who have received at least two administrations of ¹⁷⁷Lu-3BP-227 and reached the end of Cycle 2 or EOCT visit would be considered evaluable for response.

All measurable lesions up to a maximum of two lesions per organ and five lesions in total, representative of all involved organs, should be identified as target lesions and recorded and measured at baseline. Target lesions should be selected on the basis of their size (lesions with the longest diameter), be representative of all involved organs and permit reproducible repeated measurements. On occasion, if the largest lesion does not permit reproducible measurement,

the next largest lesion which can be measured reproducibly will be selected. A sum of the diameters (longest for non-nodal lesions, short axis for nodal lesions) for all target lesions will be calculated and reported as the baseline sum diameters. If lymph nodes are included in the sum, then only the short axis will be added into the sum. The baseline sum of diameters will be used as reference to further characterise any objective tumour regression in the measurable dimension of the disease.

All other lesions (or sites of disease) including any measurable lesions over and above the five target lesions should be identified as nontarget lesions and should also be recorded at baseline. Measurements of these lesions are not required, but the presence, absence, or unequivocal progression of each should be noted throughout follow-up.

Subjects will be evaluated as CR, PR, SD, PD, or inevaluable according to RECIST version 1.1. Based on this classification, the following endpoint will be calculated as defined by RECIST version 1.1 and below.

- Objective Response Rates (ORR): proportion of subjects with a best overall response (BOR) characterised as either a Complete Response (CR) or Partial Response (PR) relative to the total number of evaluable subjects
- Disease control rate (DCR): proportion of subjects with a BOR characterised as CR, PR or SD relative to the total number of evaluable subjects

The PFS and OS will also be evaluated as defined per RECIST version 1.1.

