## 2.7 **Primary population**

The primary objective of this study is safety and tolerability, therefore the primary population for analysis is the safety population.

The pharmacodynamics/efficacy analyses will be based on the pharmacodynamic population, except analyses on tumour response which will be based on the primary pharmacodynamic population and overall survival which will be based on the included population.

The Lu-3BP-227 blood pharmacokinetic analyses will be based on the Lu-3BP-227 blood Pharmacokinetic population.

The Lu-3BP-227 urine pharmacokinetic analyses will be based on the Lu-3BP-227 urine Pharmacokinetic population.

The 3BP-227 plasma pharmacokinetic analyses will be based on the 3BP-227 plasma Pharmacokinetic population.

The 3BP-227 urine pharmacokinetic analyses will be based on the 3BP-227 urine Pharmacokinetic population.

The Lu-3BP-227 pharmacokinetic analyses in discernible organs and target lesions will be based on the dosimetry population.

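### Phase I ORR and DCR have conflicting denominators in the protocol; the SAP reports only the two-dose evaluable set, which leaves out subjects who stop after one dose for toxicity or progression

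*SAP*

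**What the plan says.** The protocol answers the denominator question for phase I response in three ways.

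- The secondary endpoint in protocol 4.4.2.1 (the synopsis has the same definition) reads "Objective response rate and DCR, as determined by RECIST version 1.1 in subjects who received IMP".
- Protocol 12.1 says "All subjects who receive at least one dose of IMP and who have postbaseline efficacy data will be included in the efficacy evaluations".
- The phase I statistics part of the synopsis and protocol 12.2.7 require measurable disease and two administrations. Only subjects who meet this "and reached the end of Cycle 2 or EOCT visit would be considered evaluable for response", and ORR and DCR are then taken relative to evaluable subjects.

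The SAP adopts the third rule. Section 2.4.2 begins "The primary pharmacodynamic population for tumour response is all subjects who have received at least two therapeutic doses of" the study drug. It then requires the end of Cycle 2 or EOCT, an available post-baseline RECIST assessment, and no major protocol deviation with an impact on the analysis. Section 2.7 applies that set: "The pharmacodynamics/efficacy analyses will be based on the pharmacodynamic population, except analyses on tumour response which will be based on the primary pharmacodynamic population". No ORR or DCR is planned on any wider set. SAP section 5 reports no change from the protocol.

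**The concern.** Whether a subject receives a second dose depends partly on how the first one went. Protocol 4.7.1 ends treatment on "occurrence of a DLT for phase I dose escalation only", and section 6.2.2 says "if the disease does not appear to come under control, the subject is to be removed from study and treated as clinically indicated". Section 4.7.1.3 lets a subject who stops for progression before the end of Cycle 2 be replaced, except in Cohort 1.

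Such a subject still has an early-discontinuation (ED) visit. Protocol 6.2.2.1 gives that visit the same assessments as EOCT, and SAP 1.3.2.2 schedules the RECIST assessment there. A documented progression can therefore be collected and then left out of BOR, ORR and DCR. A treated subject with no post-baseline scan cannot appear in the BOR table at all, not even as not evaluable.

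These rates are secondary and descriptive, but they are used. Protocol 1.5 ties the choice between a basket phase II and tumour-specific Simon cohorts to whether the ORR is high or medium. SAP 3.2.24 says cohort 2 safety and efficacy tables will support the rationale for a later combination study. With three to five subjects per cohort, one or two exclusions visibly move a rate.

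**Working it through.** The plan states no rate, power or sample size that rests on this denominator, so there is no figure to reproduce. The check is a comparison of the rules, followed by an illustration.

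**Step 1: the rules side by side.** The test case is a subject with measurable disease who has one therapeutic dose and then progression on the ED scan.

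| Place | Doses needed | Other conditions | Test case counted? |
|---|---|---|---|
| Protocol synopsis endpoints and 4.4.2.1 | any IMP | none | yes |
| Protocol 12.1 | one | postbaseline efficacy data | yes |
| Protocol synopsis statistics and 12.2.7 | two | measurable disease; end of Cycle 2 or EOCT | no |
| SAP 2.4.2 | two (therapeutic) | end of Cycle 2 or EOCT; RECIST data; no impacting major deviation | no |

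Protocol 12.1 applies a deviation filter to PK and dosimetry but not to efficacy. Protocol 16.1.2 says only in general terms that major deviations may affect the analysis population.

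**Step 2: where the test case still counts.** Under SAP 2.7, PFS falls to the pharmacodynamic population (one therapeutic dose plus post-baseline data, SAP 2.4.1), and SAP 3.2.18.4 counts investigator-assessed progression and deaths. OS uses the included population. The omission is confined to BOR, ORR and DCR.

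**Step 3: possible size.** Let f be the share of treated subjects excluded, and r the response rate in the excluded divided by the rate in those kept. If the kept subjects respond at rate p, the all-treated rate is p × [(1 − f) + f × r]. The two-dose rate therefore equals the all-treated rate times

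factor = 1 / [(1 − f) + f × r].

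For f, take the mean numbers of subjects in Cycles 1 and 2 from Table 13 of protocol Attachment 5: f = 1 − (Cycle 2 / Cycle 1). In that simulation a Cycle 1 DLT bars a subject from Cycle 2. The values of r are assumptions.

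| Scenario | Cycle 1 | Cycle 2 | f | r = 0 | r = 0.5 | r = 1 | r = 1.5 |
|---|---|---|---|---|---|---|---|
| Safe | 17.5 | 15.7 | 10.3% | 1.11 | 1.05 | 1.00 | 0.95 |
| Late | 17.7 | 15.7 | 11.3% | 1.13 | 1.06 | 1.00 | 0.95 |
| Early | 18.7 | 14.3 | 23.5% | 1.31 | 1.13 | 1.00 | 0.89 |
| Peak | 15.9 | 10.8 | 32.1% | 1.47 | 1.19 | 1.00 | 0.86 |
| Toxic | 9.1 | 3.6 | 60.4% | 2.53 | 1.43 | 1.00 | 0.77 |

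Example for Early with r = 0: 1 / (1 − 0.235) = 1.31.

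An assumed all-treated ORR of 20% would be reported as 22-29% with r = 0 in the four scenarios other than Toxic (20 × 2.53 = 51% in Toxic), as 21-24% with r = 0.5 (29% in Toxic), and as 20% with r = 1.

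**Step 4: one cohort.** Suppose five are treated, three are evaluable and one responds. The all-treated rate is 1/5 = 20% (exact 95% CI 0.5-71.6%). The evaluable rate is 1/3 = 33% (0.8-90.6%). The intervals overlap almost entirely.

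Table 13 gives DLT losses only, as ratios of means. Its replacement rule differs from the study's, and progression drop-out is not in it. The shares are not forecasts.

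**The case against.** The strongest reply is that the two-dose rule is an explicit phase I rule. The synopsis and 12.2.7 address tumour response specifically, while 12.1 gives a general efficacy set, and the two can coexist: SAP 2.4.1 mirrors one and SAP 2.4.2 the other. This largely stands. A reader might infer that the SAP departs from the protocol, and the documents do not support that. What remains is that the endpoint definition in 4.4.2.1 disagrees with 12.2.7, and that the deviation filter is the SAP's own addition.

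A reader might also infer that early progressors vanish from the efficacy analysis. They do not, as Step 2 shows. RECIST data are listed by subject (SAP 3.2.18) and reasons for exclusion are tabulated (SAP 3.2.3), so an all-treated rate could be rebuilt by hand.

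Another tempting reading is that the rule breaches RECIST 1.1. Section 4.9.1 of the attached guideline does warn against a selected evaluable subset, but for phase II trials with response as the primary endpoint. Here it is guidance. Nor does listing a not-evaluable category contradict the scan requirement, since a scanned subject can still be not evaluable.

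The direction of bias is also open to challenge. Nothing in the documents shows that subjects with a DLT respond less often. That stands, and the r = 1.5 column shows the reverse case.

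Finally, an all-treated rate has weaknesses of its own. One-dose subjects did not receive the full planned activity. The schedule puts the ED visit no later than 5 weeks (35 days) after the last administration. On that latest date, stable disease meets the SAP's 56-day minimum only if the baseline scan was at least 56 − 35 = 21 days before dosing. Some subjects could therefore be called not controlled through timing alone. This supports showing both sets over replacing one with the other.

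**Conclusion.** The concern holds in a limited form and should be fixed. The protocol's denominators for phase I ORR and DCR do not agree. The SAP picks one written rule, adds an undeclared deviation filter and plans no rate on all treated subjects. Exclusion is partly outcome-related, so the two-dose rates are overstated if the excluded subjects respond, or are controlled, less often than those kept. That condition is plausible for subjects removed for progression and unproven for subjects removed for a DLT.

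On the simulated DLT losses the factor is 1.11-1.47 (2.53 in Toxic) at the extreme of no response among the excluded, 1 if they respond equally often, and below 1 if more often. It would be wrong to read any of these as the expected inflation. No type I error or power is affected, because phase I response is descriptive. The documents also do not establish that the two-dose set must lose its leading place, only that it should not stand alone.

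**What to change.** - Report BOR, ORR and DCR on the included population (at least one therapeutic dose, SAP 2.2) alongside the two-dose evaluable set, both labelled, by dose level and overall.
- In the included-population tables, count subjects without documented response or control as not responding or not controlled, and show subjects with no post-baseline scan as not evaluable. Use ED and later follow-up scans under the SAP's existing confirmation and 56-day rules.
- State that one-dose subjects did not receive the full planned activity.
- Reconcile the synopsis endpoint text and 4.4.2.1, section 12.1, and the synopsis statistics text and 12.2.7. Say whether IMP in 4.4.2.1 means the therapeutic dose, since the screening dose is also IMP.
- Declare the major-deviation filter for tumour response in SAP section 5.

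The cost is small: no new data, and extra tables on a population the SAP already uses for OS. The price is a rate that may look slightly less favourable, that includes partly treated subjects, and that needs a footnote saying so.
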